In response to the large numbers of senior center clients who suffer from untreated depression, we have partnered with the NYC Department for the Aging (DFTA) to develop SMART-MH, a community care model that can be embedded in senior centers to improve recognition, referral, and adherence to depression treatment. We also developed and tested Engage, a stepped-care therapy streamlined to use "reward exposure" as its principal intervention based on the assumption that dysfunction of the reward networks is central to the pathogenesis of depression. Mobile technology provides probes for client adherence and offers to therapists easy to review summary records of mood, activity, and social interaction that can be used to target their sessions. We integrated SMART-MH and Engage-M into a comprehensive community care model "Reaching and Engaging Depressed Senior Center Clients" (REDS). In REDS Phase II, we plan to introduce behavioral economics principles to increase adherence to interventions and to the use of mobile technology active ratings and passive sensing of behavior. Augmented Engage (Engage-A) will be offered to patients in this study. This treatment is similar to Engage-M, but augmented with mobile technology and behavioral economics. During the peak of the COVID 19 pandemic, we were unable to offer group sessions but continued to monitor our depressed participants remotely. Our impression has been that depressed participants were happy to hear from us and eager to engage in remote sessions. These observations led to our decision to retain the SMART-MH as part of REDS because it made identification and referral to care organic to the senior centers' function. However, we decided to change the format of Engage into individual, virtually administered sessions and augment it with mobile technology and incentives to adhere to treatment assignments based on principles of behavioral economics.

Sample Size: Patient/Subjects N = 60

Therapist/subjects N= 10

Study Population: The study will include adults (ages 49+, all genders), who are experiencing symptoms of depression.

Enrollment Period: 12 weeks

Study Design

Senior centers will offer "Augmented Engage (Engage-A)," which is Engage, the treatment offered by REDS, augmented with a mobile technology and behavioral economics . The intervention consists of 9

individual sessions (sessions 1 through 9). These sessions can be in-person, over the phone, or over video call.

The principal intervention of Engage-A is “reward exposure” with additional interventions (for negativity bias, apathy, or emotional distress) for participants with barriers to “reward exposure”. Participants are instructed to use a Pocket Weekly Planner (on paper) to schedule a rewarding activity daily and also record preparatory steps. In each week, at least one of the activities should be done with a person important to the patient and at least one activity should be expected to generate a sense of accomplishment. We based this decision on an analysis of Engage study preliminary data, which showed that a higher percentage of interpersonal-individual activities (but not solitary or social-group activities) predicted subsequent increase in behavioral activation and improvement of depression (Solomonov et al *Am J Geriatr Psychiatry*, 2019 Jan 10. pii: S1064-7481(19)30006-5. doi: 10.1016/j.jagp.2018.12.033).

Study Location

New York Presbyterian Westchester Division, [name]; Council Center for Senior Citizens [name]; JCC of Staten Island [name]; United Senior Center of Sunset Park [name]; Diana H. Jones Innovative Senior center [name]; JCC Center You Avis Neighborhood Senior Center [name]

Participants

The participants will have clinically significant depressive symptoms (PHQ-9 \geq 10) and will be older and middle-aged adults (55+). This study will recruit from four senior centers overseen and funded by the Department for the Aging in New York City.

Objectives: The specific aims of this developmental project are to: 1. Examine reach, feasibility, and acceptability of REDS II; 2. Examine engagement of behavioral targets and preliminary effectiveness; and 3. Collect information on REDS II cost, barriers to implementation, and potential savings in health care utilization.

1.1 Study Objectives

1.1.1 Objectives: The specific aims of this developmental project are to: 1. Examine reach, feasibility, and acceptability of REDS II; 2. Examine engagement of behavioral targets and preliminary effectiveness; and 3. Collect information on REDS II cost, barriers to implementation, and potential savings in health care utilization.

1.1.2 Hypotheses/Research Questions: Primary: H1) More than 80% of Virtual ENGAGE-A participants will attend each scheduled session. H2) Seniors will have an average satisfaction (CSQ) score greater than 3 (out of 4) at 3, 6, and 12 weeks follow-up. H3) Community clinicians (LCSW) will have an average satisfaction (CSQ) score greater than 3 (out of 4) at the end of the study.

Secondary: Compared to ENGAGE (9 sessions, in-person), Virtual ENGAGE-A participants will have: SH1) Greater (effect size) and clinically significant reductions in depressive symptoms ($\Delta \geq 3$ pts difference in 24-item HAM-D over 12 weeks); SH2) In the Virtual Engage-A group, increase in behavioral activation (Activation subscale of the Behavioral Activation for Depression Scale) will be followed by reduction in subsequent depression scores (HAM-D); and SH3) in quality of life [Primary Outcome: WHOQL-BREF].

Comparisons with Virtual ENGAGE-A: In addition to the above comparisons we will compare the reach, feasibility, acceptability, preliminary effectiveness, and target engagement of Engage-A with those of Engage-M administered in a group format.

2. Background and Significance: Approximately 10,000 senior centers operate in the US and serve 1.25 million persons nationwide. Most of their clients have low income, and in NYC, 68% are non-Caucasian. About 10% have clinically significant depression⁵ but most receive no care⁶. We developed SMART-MH, a community care model that can be embedded in senior centers to improve recognition of depression, referral, and adherence to depression treatment. We also developed Engage, a stepped-care therapy, streamlined based on the assumption that a dysfunction of the reward network is central to the pathogenesis of depression and using "reward exposure" as its principal intervention. Engage also targets negativity bias, apathy, and inadequate emotion regulation if they act as barriers to reward exposure. Mobile technology provides probes for client adherence and offers to therapists easy to review summary records of mood, activity, and social interaction that can be used to target their sessions. We integrated the SMART-MH model and Engage-M into a comprehensive community care model "Reaching and Engaging Depressed Senior Center Clients" (REDS). In REDS Phase II, we plan to introduce behavioral economics principles to increase adherence to interventions and to the use of mobile technology active ratings and passive sensing of behavior. Augmented Engage (Engage-A) will be offered to patients in this study. This treatment is similar to Engage-M, but augmented with mobile technology and behavioral economics. During the peak of the COVID 19 pandemic, we were unable to offer group sessions but continued to monitor our depressed participants remotely. Our impression has been that depressed participants were happy to hear from us and eager to engage in remote sessions. These observations led to our decision to retain the SMART-MH as part of REDS because it made identification and referral to care organic to the senior centers' function. However, we decided to change the format of Engage into individual, in-person or virtually

administered sessions and augment it with mobile technology and incentives to adhere to treatment assignments based on principles of behavioral economics. Our relationship with the NYC Dept. for Aging (DFTA) offers the opportunity to embed and rapidly deploy REDS in NYC Senior Centers, and may make the REDS model part of a sustainable service reimbursable by Medicare.

3. Study Design and Methods

Overall Design:

Senior centers will offer “Augmented Engage (Engage-A),” which is Engage, the treatment offered by REDS, augmented with a mobile technology and behavioral economics. The intervention consists of 9 individual sessions (sessions 1 through 9). The sessions can be in-person, over the phone, or over video call.

Intervention: The principal intervention of ENGAGE-A is “reward exposure” with additional interventions (for negativity bias, apathy, or emotional distress) for participants with barriers to “reward exposure”. Participants are instructed to use a Pocket Weekly Planner (on paper) to schedule a rewarding activity daily and also record preparatory steps. In each week, at least one of the activities should be done with a person important to the patient and at least one activity should be expected to generate a sense of accomplishment. We based this decision on an analysis of ENGAGE study preliminary data, which showed that a higher percentage of interpersonal-individual activities (but not solitary or social-group activities) predicted subsequent increase in behavioral activation and improvement of depression (Solomonov et al *Am J Geriatr Psychiatry*, 2019 Jan 10. pii: S1064-7481(19)30006-5. doi: 10.1016/j.jagp.2018.12.033). We plan to introduce behavioral economics principles to increase adherence to interventions and to the use of mobile technology active ratings and passive sensing of behavior. This approach has not been used in mid- and late-life depression, but there is significant literature from U Penn showing that older, medical patients (obese or patients with ischemic heart disease) can meet health behavior goals using this approach (please see <https://www.waytohealth.org/publications>). A Booklet will be used as a reference by participants to ENGAGE A (in **Appendix to REDS**). The Booklet outlines concepts on depression and on “reward exposure”, and offers examples of meaningful rewarding activities (i.e. activities with a person important to participant, activities likely to give a sense of accomplishment, self-care activities, pleasurable activities, and social group activities) and gives examples of preparatory steps likely to be needed before each planned activity. In addition, the Booklet describes interventions for barriers to reward exposure (for negativity bias, apathy, or emotional distress). Therapists identify a barrier specific to an individual participant, if one exists, teaches the participant how to use the intervention corresponding to the barrier, points out the Booklets section describing the intervention and helps participants to schedule and practice each intervention in their Pocket Weekly Planner.

3.1 Mobile Technology: Mobile technology is designed to augment the in-person or remote sessions of Engage-A. A smart phone and a Withings watch will be the vehicles for mobile technology interventions.

3.1.1 Augmentation of Engage-A consists of:

- 1) Daily ratings of mood, interest or pleasure in activities, stress, and pain. A text message sent by Way to Health prompts participants to rate these 4 items on a scale of 1 to 10.
- 2) Daily reminders to pursue preparatory steps and scheduled meaningful, rewarding activities.

- 3) Passive sensing of movement (steps) and sleep daily. Participants are reminded to review their step count and deep and light sleep duration daily and receive a weekly summary of both on Fridays.
- 4) Participants receive a text message at 7 pm asking them whether they engaged in their daily planned activity and to rate the sense of pleasure (scale 1 to 10) and the sense of satisfaction (scale 1 to 10) they derived.
- 5) At the end of each week, participants receive a text message indicating to them the reward level they achieved. Based on studies of non-depressed older adults by U. Penn investigators, we are using an incentive plan based on the following behavioral economics principles: Loss is valued more than gain, variable reinforcement is more effective than constant reinforcement, “fresh start” increases desirable behavior, and long term-gains are reinforcing. Accordingly, patients are given 100 points on each Monday and they will be rewarded if they can keep these points by pursuing their scheduled activities. They lose 10 points each time they fail to perform and record their daily activity. All patients start at the Silver level. If a patient has 70 points at the end of a week (Sunday), he/she advances to a higher level (gold, platinum). Patients are informed that if they finish the study at the Gold level they will receive a \$50 gift certificate.

4. Study Design

4.1 **Study Population:** The study population involves seniors (aged at least 55 years) with depression.

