7. **Statistical Considerations:** Senior center staff will refer participants they believe may benefit from the intervention. Due to COVID-19, recruitment will occur remotely, and participants can be referred from wellness calls made by our clinicians as well as from 311 calls. Flyers and advertisements will also be used for recruitment. We will be recruiting 60 subjects in total from the site (WCMC only site) and six licensed clinical social worker subjects. 1. Recruitment and referral sources: We are working with [name] and [name] of the NYC Department for the Aging (DFTA) to plan implementation of the REDS project at 4 NYC senior centers. Older and middle-aged (55+) senior center clients with elevated depressive symptoms (LCSW training phase n=10 clients; Effectiveness Pilot n=60) will be recruited from the 4 participating senior centers. Clients in the startup phase, during which LCSWs are trained, will be recruited from each of 2 centers randomly assigned to REDS (n=10) over a 4-month period. 60 clients will be recruited to the Engage-A intervention over approximately a 14-month period. We have chosen to partner with senior centers that represent clients from diverse backgrounds. Each partnering senior center documents at least 800 active members each, with a daily participation rate of at least 200 members. Given an expected 10% rate of eligible clients (PHQ-9 > 10), we expect at least 80 clients at each center to meet inclusion criteria to be referred to the study. Excluding those with severe mental illness or dementia as assessed via research measures, we anticipate that over 60 clients at each center will meet inclusion criteria for the RCT. This study will recruit from four senior centers overseen and funded by the Department for the Aging in New York City.

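### SH1 and SH3 compare Engage-A with in-person ENGAGE, but all 60 clients receive Engage-A and no comparator source or analysis is stated, so the design cannot support a conclusion of greater benefit

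*Combined protocol and SAP*

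**What the plan says.** Section 1.1.2 opens the secondary hypotheses with "Compared to ENGAGE (9 sessions, in-person), Virtual ENGAGE-A participants will have: SH1) Greater (effect size) and clinically significant reductions in depressive symptoms". The size attached to SH1 is at least 3 "pts difference in 24-item HAM-D over 12 weeks". SH2 is stated within the Engage-A group only. The last item reads "SH3) in quality of life [Primary Outcome: WHOQL-BREF", closing the bracket there; it has no verb or direction of its own and draws its meaning from the comparative stem. The next paragraph confirms that comparisons are meant and adds one with group-format Engage-M: "In addition to the above comparisons we will compare the reach, feasibility, acceptability, preliminary effectiveness, and target engagement of Engage-A".

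The design text describes a single treatment. The synopsis says "Augmented Engage (Engage-A) will be offered to patients in this study", section 3 (Overall Design) describes only Engage-A, and section 7 says "60 clients will be recruited to the Engage-A intervention over approximately a 14-month period". Sixty is the whole client sample given in the synopsis, apart from the 10 clients in the training phase for social workers.

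Earlier work is mentioned. The synopsis says "We also developed and tested Engage, a stepped-care therapy streamlined to use" reward exposure as its main component, and refers to "an analysis of Engage study preliminary data, which showed that a higher percentage of interpersonal-individual activities" predicting later improvement. That second reference justifies the choice of activities. Neither passage names a comparison dataset.

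**The concern.** SH1 is directional: it expects Engage-A to reduce depressive symptoms more than in-person ENGAGE does. A reader following the plan would compute a difference against some ENGAGE figure and, if it pointed the right way, report that Engage-A was better. With one treatment in the study, that figure has to come from outside. The plan does not say from where, from how many people, or how the two groups would be made comparable. The choice would then be open after the Engage-A results are known.

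An external group may differ from these 60 clients in calendar period and case mix. Section 4.4 describes remote recruitment for this study because of COVID-19, with referral from wellness calls and 311 calls. If the groups differ, an apparent advantage could reflect when and from whom clients were recruited. Equally, a real advantage could be hidden. Aim 2 includes preliminary effectiveness and SH1 is its depression outcome, so the matter is not marginal even though it is secondary.

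**Working it through.** **No figure to reproduce.** The plan gives 60 clients without a significance level, power, SD, comparator size or dropout rate. The finding rests on setting the sections side by side:

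- Comparison asserted: section 1.1.2, with ENGAGE for SH1 and SH3, and with Engage-M in the paragraph after.
- Treatment received: Engage-A for all 60 (synopsis, section 3, section 7).
- Comparator source: none named anywhere.
- Analysis: section 7, Statistical Considerations, holds recruitment text only. Section 5, Data Collection, is a heading with no text beneath it, and nothing there is marked as redacted.
- Randomisation: sections 4.4 and 7 use the term RCT, and section 7 says 2 start-up centers are randomly assigned to REDS. No alternative condition, arm or ratio is given.

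The comparison therefore has one side only.

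**Illustration of what an uncorrected cohort difference could do.** Every input below is an assumption except the 60 clients.

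- SD of 12-week HAM-D change: 6 to 8 points. Comparators m: 30 to 100. True effect: 0. Cohort difference d: 2 points in Engage-A's favour.
- Standard error = SD × √(1/60 + 1/m). Chance that the observed difference favours Engage-A = Φ(d/SE).
- SD 8, m = 30: SE = 8 × √(0.01667 + 0.03333) = 1.79; 2/1.79 = 1.12; Φ = 0.868.
- SD 6, m = 100: SE = 6 × √(0.01667 + 0.01000) = 0.98; 2/0.98 = 2.04; Φ = 0.979.
- Range: 87% to 98%, against 50% when d = 0.
- Other values of d: 71% to 85% for 1 point and 95% to 99.9% for 3 points.
- Opposite direction, d = 2 against Engage-A: 1 − 0.979 to 1 − 0.868, or 2% to 13%.

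In this calculation a larger comparator group pushes the probability further from 50%. Size does not remove a cohort difference.

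**Precision of the alternative.** The 95% CI half-width for mean within-group change is t(0.975, n−1) × SD/√n. With n = 60 this is 1.55 points at SD 6 and 2.07 at SD 8. If 20% were lost (an assumption), n = 48 gives 1.74 and 2.32.

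**Entry criteria for choosing external participants.** The synopsis gives age 49+ under Study Population and 55+ under Participants; sections 4.1 and 4.2 give 55. The synopsis and section 4.2 give PHQ-9 of 10 or higher; sections 4.4 and 7 give above 10. As written, an external group could not be matched to one set of criteria.

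**The case against.** **It is called an RCT.** The term appears in sections 4.4 and 7, and a reader might infer that a control arm exists and is merely undescribed. The documents do not support that. Section 7 sends all 60 clients to Engage-A, and the random assignment concerns the 10-client start-up phase with no alternative named. This is a consistency problem and does not supply a control.

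**Earlier Engage data are plainly intended.** That may be so, and an external comparison with a named source, adjustment and interval is legitimate. This much stands, and the fix keeps such a comparison. It remains non-randomised, and the plan does not name the source or the method.

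**The bias is not shown.** This stands. A reader might infer from section 4.4 that recruitment changed between the earlier cohorts and this one, or that the comparison would be tilted towards Engage-A. The documents do not say when or how earlier ENGAGE or Engage-M participants were recruited, so neither the existence, the direction nor the size of a bias is established. The percentages above show what assumed values would imply and do not estimate this study's error.

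**The 3-point figure could be a within-group change.** This is possible, but under a stem that compares with ENGAGE the natural reading is a between-treatment difference. The point does not rely on the other reading.

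**These are secondary hypotheses in a developmental project.** This stands as to weight. A reader might infer that the study as a whole is compromised. It is not: H1 to H3 are judged against fixed thresholds for attendance and satisfaction, and SH2 is within the Engage-A group.

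**Conclusion.** The concern holds for SH1, for SH3 through its stem, and for the added Engage-M comparison. With a single treatment and no stated comparator or analysis, a conclusion that Engage-A produces greater benefit is not supported. This follows from the text alone and needs none of the assumed values. The 87% to 98% range holds only for an assumed SD of 6 to 8, 30 to 100 comparators, no true effect and a 2-point cohort difference favouring Engage-A.

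The point should be corrected, ideally before any results are seen, but it is not a fatal flaw: it touches secondary hypotheses only.

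**What to change.** 1. Make the main SH1 estimate the mean HAM-D change within Engage-A from baseline to week 12, with a 95% CI. Report it descriptively and not as a treatment effect: clients enter on a raised PHQ-9, so some improvement from regression to the mean is expected. Do the same for WHOQL-BREF in SH3, after completing its wording and confirming when it is assessed, which is not stated.
2. Keep any ENGAGE or Engage-M comparison only as a non-randomised external comparison, with its source named before results are known. If patient-level data exist, give the difference in HAM-D change adjusted for baseline HAM-D, with a 95% CI; otherwise set summary figures alongside. Do not present either as evidence that Engage-A is superior.
3. State that the 3-point figure is not a success criterion in this single-treatment design.
4. Reconcile the age and PHQ-9 entry criteria before using them to select external participants, and reconcile the RCT and random-assignment wording with the single-treatment design.

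**Cost.** Mainly wording. No extra clients or visits are needed, since section 6.3 already lists baseline and week-12 assessments. It names no instruments, however, so WHOQL-BREF may have to be added to an existing visit. The adjusted comparison is extra work only if patient-level external data exist, which the documents do not show. The downside is a weaker comparative claim.

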4.2 Inclusion Criteria

Criteria Referral to study:

1. Age at least 55 years.
2. PHQ-9 score of 10 or higher via routine screening by senior center staff
3. English or Spanish speaking.
4. Capacity to provide written consent for both research assessment and the Engage-M intervention.

